### ***Weekly Patient Assessment of Constipation Severity***

Patient assessment of constipation severity will be reported weekly by eDiary entry. The rating of constipation severity during the previous 7 days on a 5-point ordinal scale will be provided by the patient answering the following question:

“On average, how would you rate your constipation during the past 7 days?”

- 1=None
- 2=Mild
- 3=Moderate
- 4=Severe
- 5=Very severe

### ***Weekly Patient Assessment of IBS Symptom Severity***

Patient assessment of IBS symptom severity will be reported weekly by eDiary entry. The rating of IBS symptom severity during the previous 7 days on a 5-point ordinal scale will be provided by the patient answering the following question:

“On average, how would you rate your IBS symptoms during the past 7 days?”

- 1=None
- 2=Mild
- 3=Moderate
- 4=Severe
- 5=Very severe

### ***Weekly Patient Assessment of Adequate Relief***

Patient assessment of adequate relief of IBS symptoms will be reported weekly by eDiary entry. The rating of adequate relief during the previous 7 days on a binary scale will be provided by the patient answering the following question:

“Overall, have you had adequate relief from your IBS symptoms during the past 7 days?”

1=Yes  
2=No

### ***Weekly Patient Assessment of Treatment Satisfaction***

Patient assessment of treatment satisfaction will be reported weekly by eDiary entry each week after the Randomization Visit. Patients will answer the following question on a 5-point ordinal scale:

“Overall, how satisfied are you with the study medication’s ability to relieve your IBS symptoms?”

1=Not at all satisfied  
2=A little satisfied  
3=Moderately satisfied  
4=Quite satisfied  
5=Very satisfied

## **5.3.4            Health Outcomes Assessments**

### ***5.3.4.1            IBS-QOL***

The IBS-QOL is an instrument for assessing the impact of IBS on a patient’s quality of life ([Appendix 2](#)). The IBS-QOL will be completed at the Randomization Visit prior to the patient receiving study drug and at subsequent visits as specified in the Schedule of Evaluations ([Table 5.1-1](#)). At each of the designated visits, the assessment will be triggered by site personnel on the patient’s eDiary for the questionnaire to be self-administered by the patient.

### ***5.3.4.2            CDC Healthy Days Core Module (CDC HRQOL-4)***

The CDC Healthy Days Core Module (CDC HRQOL-4; [Appendix 3](#)) assesses a person’s perceived health status through 4 questions that assess self-rated health, numbers of recent days when physical health or mental health was not good, and number of recent days with limitations due to poor physical or mental health. For the CDC HRQOL-4 items, recent is defined as during the past 30 days. The CDC HRQOL-4 will be completed at the Randomization Visit prior to the patient receiving study drug and at subsequent visits as specified in the Schedule of Evaluations ([Table 5.1-1](#)). At each of the designated visits, the assessment will be triggered by site personnel on the patient’s eDiary for the questionnaire to be self-administered by the patient.

## 5.4 SAFETY ASSESSMENTS

The safety parameters will include adverse events (AEs), clinical laboratory and vital sign parameters, and physical examination.

### 5.4.1 Adverse Events

The AE assessment (interview) will be collected from the time the patient signed the informed consent obtained until completion of trial participation (eg, early termination or Week 16/EOT Visit). At each trial visit, the investigator will inquire about the occurrence of AEs/SAEs since the last visit.

#### 5.4.1.1 Causality Assessment

Causal relationship must be assessed according to the following scale:

- Related An AE is attributed to the study medication if:
  - A temporal relationship to study drug administration makes a causal relationship plausible (eg, the event occurred within a reasonable time frame following administration of study medication); and/or
  - Other causative factor(s) (eg, the subject's clinical condition, other concomitant treatments) either do not explain the event or are less equally likely to have led to the occurrence of the event, or
  - The event improved with stopping of the investigational product, and/or
  - The event recurred upon re-exposure with investigational product
- Not Related Any other event (refer to [Section 8.2.1.2.2 of the protocol](#) for details)

#### 5.4.1.2 Severity Assessment

Severity will be assessed according to the following scale:

- Mild A type of AE that is usually transient and may require only minimal treatment or therapeutic intervention. The event does not generally interfere with usual activities of daily living.
- Moderate A type of AE that is usually alleviated with additional specific therapeutic intervention. The event interferes with usual activities of daily living, causing discomfort, but poses no significant or permanent risk of harm to the research participant.
- Severe A type of AE that interrupts usual activities of daily living, or significantly affects clinical status, or may require intensive therapeutic intervention.

#### **5.4.1.3        Serious Adverse Events**

All adverse events will be categorized as Serious (as defined in the [MCP-103-312 Protocol, Section 8.2.1.1](#)) or Non-Serious.

#### **5.4.2        Medical History**

A complete medical history will be performed as defined in the Schedule of Evaluations ([Table 5.1-1](#)).

#### **5.4.3        Physical Examination**

A complete physical examination will be performed as defined in the Schedule of Evaluations ([Table 5.1-1](#)). A physical examination will include the following assessments: general appearance; head, ears, eyes, nose, and throat (HEENT); neck; cardiovascular; thorax/lungs; abdomen; musculoskeletal; lymph nodes; skin; neurologic; and mental status. Breast, genitourinary, and rectal examinations are optional at the discretion of the investigator, except as described in the Schedule of Evaluations ([Table 5.1-1](#)).

#### **5.4.4        Vital Signs**

Vital sign measurements will be performed as defined in the Schedule of Evaluations ([Table 5.1-1](#)). Vital sign measurements include oral temperature (°C), respiratory rate, systolic and diastolic blood pressure (BP), and pulse. Pulse and BP readings will be taken after the patient has been seated for at least 5 minutes.

#### **5.4.5        Clinical Laboratory Data**

Fasted blood and urine samples for clinical laboratory tests will be collected at the days and times defined in the Schedule of Evaluations ([Table 5.1-1](#)). A central laboratory will be used to evaluate all blood and urine samples (except the urine pregnancy test).

The following clinical laboratory tests will be performed:

**Hematology:** Absolute and differential white blood cell count, erythrocyte count, hemoglobin, hematocrit, platelet count, and red blood cell indices (mean corpuscular volume, mean corpuscular hemoglobin, and mean corpuscular hemoglobin concentration)

**Chemistry:** Sodium, magnesium, potassium, calcium, chloride, glucose, blood urea nitrogen, creatinine, total protein, alkaline phosphatase, albumin, total bilirubin, aspartate aminotransferase, alanine aminotransferase, bicarbonate, phosphate, cholesterol, and uric acid

**Other:** Urine drug screening (cocaine, barbiturates, amphetamines, opiates, benzodiazepine, alcohol, and cannabinoids) (Screening Visit only). Clinical significance of a positive urine drug screen will be assessed by the investigator; positive results for cocaine, barbiturates, and cannabinoids are exclusionary.

**Pregnancy test:** Serum human chorionic gonadotropin pregnancy test (for women of childbearing potential only) should be conducted at the Screening Visit and Week 16/EOT Visit. A negative urine pregnancy test must be documented at the Randomization Visit and the Week 12/ETP Visit for the patient to be eligible for randomization and dosing with study drug. Positive results on the pregnancy test will exclude a patient from participating or continuing in the trial.

## **6.0 STATISTICAL METHODS**

### **6.1 GENERAL METHODS**

Efficacy outcomes from the Treatment Period will be based on the ITT Population and will be summarized by treatment group assigned at the Randomization Visit. Efficacy outcomes from the RW Period only or from the Combined Treatment and RW Period will be based on the RW Population and will be summarized by treatment sequence determined at the Week 12/ETP Visit. Treatment periods will be summarized for safety in the same manner as efficacy; however, safety summaries (Safety Population) will be based on the actual treatment received.

Descriptive statistics including the number of patients, mean, minimum and maximum, and standard deviation (SD) will be calculated for continuous variables. Frequencies and percentages for each category will be calculated for categorical variables. Percentages will be based on the total number of non-missing values. The number missing will be presented, but without a percentage. All hypothesis tests will be two-sided with a 5% significance level, and 95% confidence intervals (CIs) will be used, unless stated otherwise.

All statistical analyses will be performed using SAS Version 9.3 (or later) for Windows.

### **6.2 ADJUSTING FOR COVARIATES**

As a general approach, the baseline values will be included in the mixed model for repeated measures (MMRM) and analysis of covariance (ANCOVA) as a covariate when the postbaseline or change scores are analyzed. Heterogeneity of slopes will be explored (e.g., review of residuals, inclusion of an interaction term, comparison of group differences at the 25th and 75th percentiles).

### **6.3 HANDLING OF DROPOUTS/MISSING DATA IMPUTATION METHOD**

For responder endpoints, a patient will be deemed a weekly non-responder for all weeks following the patient's discontinuation from the study. The responder definition will be applied to the week the patient discontinues. Unless stated otherwise, missing data will not be imputed.

### **6.4 INTERIM ANALYSIS AND DATA MONITORING**

No formal interim analyses are planned to compare treatment groups with respect to efficacy or safety prior to formal completion of the trial.

### **6.5 MULTICENTER STUDIES**

This study is being conducted in approximately 80 centers. Due to the potential of small numbers of patients per center, data will be pooled into the following 5 geographic regions (as listed in Section 9.3): Northeast, Southeast, Midwest, Southwest, and West.

All analyses using trial center will use this 5-category geographic region variable.

## **6.6 MULTIPLE COMPARISONS/MULTIPLICITY**

The overall family-wise Type I error rate for the primary and secondary efficacy analyses will be controlled at the  $\alpha=0.05$  level by employing a fixed-sequence procedure as described below. Following the fixed-sequence procedure, if the primary hypothesis between the placebo group and the linaclotide 290  $\mu\text{g}$  group is statistically significant ( $\alpha=0.05$ ) in the ITT Population, then the primary objective of the trial will have been achieved and the next hypothesis can be tested; otherwise, testing will stop. The testing of each sequential hypothesis is conditional on all the previous hypotheses being rejected at the 0.05 level of significance. If a hypothesis is not rejected at the 0.05 level of significance, then all remaining hypotheses are deemed not statistically significant. All hypothesis testing will be two-sided.

1. Linaclotide vs. placebo – Change from Baseline in Abdominal Score
2. Linaclotide vs. placebo – Change from Baseline in 12-week Abdominal Score (CDF)
3. Linaclotide vs. placebo – 6/12 Week Abdominal Score Responder
4. Linaclotide vs. placebo – Change from Baseline in Abdominal Score at Week 12
5. Linaclotide vs. placebo – Change from Baseline in Abdominal Score at Week 10
6. Linaclotide vs. placebo – Change from Baseline in Abdominal Score at Week 8
7. Linaclotide vs. placebo – Change from Baseline in Abdominal Score at Week 6
8. Linaclotide vs. placebo – Change from Baseline in Abdominal Score at Week 4
9. Linaclotide vs. placebo – Change from Baseline in Abdominal Score at Week 2
10. Linaclotide vs. placebo – Change from Baseline in Abdominal Score at Week 1

## **6.7 USE OF AN EFFICACY SUBSET**

Not applicable

## **6.8 ACTIVE CONTROL TO SHOW EQUIVALENCE**

Not applicable.

## **6.9 EXAMINATION OF SUBGROUPS**

Subgroup analyses will be performed on the primary and secondary efficacy endpoints, as well as treatment emergent adverse events by preferred term using the subgroups defined in [Table 6.9-1](#).

**Table 6.9-1 Subgroup Variables**

Subgroup Variable	Subgroups
Age	(1) $<65$ ; $\geq 65$ (2) $<65$ ; $\geq 65$ to $<75$ ; $\geq 75$
Sex	Female; Male
Race	Caucasian; Black/African American; Other
Ethnic Origin	Hispanic; Non-Hispanic
Body Mass Index (BMI)	$<30 \text{ kg/m}^2$ ; $\geq 30 \text{ kg/m}^2$

## **7.0 ANALYSIS METHODS**

### **7.1 PATIENT POPULATIONS**

#### **7.1.1 Screened Population**

The Screened Population consists of all patients who signed informed consent and received a patient identification (PID) number.

#### **7.1.2 Safety Population**

The Safety Population consists of all patients who received at least one dose of study drug.

#### **7.1.3 Intent-to-Treat Population**

The Intent-to-Treat (ITT) Population consists of all randomized patients. Efficacy analysis will be based on the ITT population, in which patients are evaluated according to the treatment group to which they were assigned at randomization.

#### **7.1.4 Randomized Withdrawal Population**

The RW Population consists of all patients who were re-randomized or allocated to study drug upon completion of the Treatment Period. For the RW Period, there are 3 treatment sequences as follows:

1. **290 µg-290 µg** (290 µg linaclotide administered in the Treatment Period, followed by 290 µg linaclotide in the RW Period)
2. **290 µg-Placebo** (290 µg linaclotide administered in the Treatment Period, followed by placebo in the RW Period)
3. **Placebo-290 µg** (placebo administered in the Treatment Period, followed by 290 µg linaclotide in the RW Period)

#### Randomized Withdrawal Safety Population

The RW Safety Population consists of all patients who were re-randomized to or assigned to double-blind RW treatment and received at least one dose of RW treatment.

## **7.2 PROTOCOL DEVIATIONS**

Protocol deviations and Important Protocol Deviations (IPD) will be identified and documented for all randomized patients prior to unblinding through programmatic checks of the study data and select individual data reviews. IPDs will be determined based on review of all protocol deviations and protocol deviation categories (i.e., Use of Disallowed Medication); this review will be performed by members of the Ironwood Clinical Trials team, including but not limited to the Clinical Medical Researcher and study Biostatistician. IPD categories include, but are not limited to:

- those who entered the study even though they did not satisfy the entry criteria
- those who developed withdrawal criteria during the study but were not withdrawn
- those who received the wrong treatment or incorrect dose

- those who received an excluded concomitant treatment

The number and percentage of subjects with IPDs will be presented by study treatment and IPD category. Protocol deviations and IPDs will be provided by patient in data listings.

### 7.3 PATIENT DISPOSITION

The number and percentage of patients included in each of the Safety, and ITT populations will be summarized overall and by treatment group for each trial center within each geographic region. The number of patients in the Screened Population will be summarized by geographic region (See Section 9.3 for definition of geographic region) and by study center.

The number and percentage of screen failure patients (i.e., patients who entered the Screening Period but not the Pretreatment Period) and the number and percentage of pretreatment failures (i.e., patients who entered the Pretreatment Period but were not randomized), along with the associated reasons for failure, will be tabulated overall for the Screened Population. Patients who initially failed screening and were re-screened will only be counted once, that is, the PID used for the rescreened subject will be summarized and listed for patient disposition.

The number and percentage of ITT patients, the number and percentage of patients who completed the Treatment Period, as well as the number and percentage of patients who prematurely discontinued treatment will be presented for each treatment group and pooled across treatment groups. The reasons for premature discontinuation from the Treatment Period as recorded on the trial completion forms of the electronic case report forms (eCRFs) will be summarized (number and percentage) by treatment group for the Randomized Population. The number and percentage of patients who prematurely discontinued treatment will be summarized for each treatment group by time of discontinuation, defined as the number of days from first dose of study drug to the date of last dose during the Treatment Period, categorized into weeks (Week 1 through Week 12). All patients who prematurely discontinue during the Treatment Period will be listed by discontinuation reason for the Randomized Population.

Similar to the Treatment Period, the number and percentage of patients who are re-randomized into the RW Period, complete the RW Period, and prematurely discontinue from the RW Period will be presented overall and by treatment sequence. The reason for premature discontinuation from the RW Period as recorded on the trial completion forms of the eCRFs will be summarized (number and percentage) by treatment sequence and overall.

### 7.4 DEMOGRAPHICS AND OTHER BASELINE CHARACTERISTICS

Demographic parameters (age, age group, race, ethnicity, sex), and baseline characteristics (weight; height; and body mass index, calculated as weight in kg/[height in m]) will be summarized descriptively for the Safety and ITT Populations. Baseline efficacy parameters (including the abdominal score, abdominal bloating, abdominal discomfort, abdominal pain, SBM frequency, CSBM frequency, BSFS score, stool consistency, and straining) will be summarized descriptively for the ITT Population.

Abnormalities in patients' medical and surgical histories will be coded using the Medical Dictionary for Regulatory Activities (MedDRA), version 21.0. The number and percentage of patients with abnormalities in medical and surgical histories in each system organ class (SOC) and preferred term will be summarized by treatment group for the Safety Population.

## **7.5 MEASUREMENT OF TREATMENT COMPLIANCE**

Dosing compliance for a specified period is defined as the total number of capsules taken by a patient during that period divided by the number of capsules that were expected to be taken during the same period, multiplied by 100. The total number of capsules taken will be calculated based on the following equation: total number of capsules dispensed – (number of capsules returned + number of capsules lost). The total number of capsules expected to be taken during a specified period equals the number of days in the period.

Descriptive statistics for study drug compliance for the Treatment Period overall, and for each of the 3 consecutive 4-week periods (weeks 1-4, 5-8, 9-12) in the Treatment Period (consistent with study drug dispensing) will be presented for the Safety Population. Similarly, descriptive statistics for the RW Period (RW weeks 1-4) will be presented for the RW Population.

## **7.6 EXTENT OF EXPOSURE**

Exposure to study drug will be calculated as the number of days from the date of first dose taken to the date of last dose taken.

Exposure to study drug for the Safety Population during the double-blind treatment period will be summarized descriptively by treatment group. Overall treatment duration will also be categorized as 1 Day; >1 Day to  $\leq$  7 Days; >7 Days to  $\leq$  30 Days; >30 Days to  $\leq$  90 Days; and >90 Days and the number and percent of patients in each category will be summarized. In addition, a cumulative distribution graph of exposure to study drug by treatment will be provided.

Patient-years, defined as exposure to the study drug in years, will be summarized by treatment group for the Safety Population.

Similar summaries will be provided by treatment sequence for the RW period with the Overall treatment duration categorized as 1 Day; >1 Day to  $\leq$  7 Days; >7 Days to  $\leq$  21 Days; >21 Days to  $\leq$  28 Days, and >28 Days.

## **7.7 PRIOR AND CONCOMITANT MEDICATION**

Prior medication is defined as any medication taken before the date of the first dose of double-blind study drug. Concomitant medicines are defined as any medicines taken on or after the date of first dose of study drug during the defined period (Treatment/RW). Any medicines started after the date of last dose of study drug for the defined period (Treatment/RW) will be excluded from the summaries related to concomitant medicines for that period.

Both prior and concomitant medications will be coded by drug name and therapeutic class using WHO Drug B2 March 2018 version or above. The use of prior and concomitant medications will be summarized for the Safety Population by the number and percentage of patients in each treatment group and for the RW Population by treatment sequence receiving each medication within each therapeutic class. If a patient took a specific medication multiple times or took multiple medications in the same category (based on Anatomical-Therapeutic-Chemical classification), that patient would be counted only once for the coded drug name or therapeutic class. The use of per-protocol rescue medicines is collected separately in the eDiary and will be summarized as described in Section 7.9.3.

## 7.8 EDIARY COMPLIANCE

Patients are required to enter their evening diary assessments into the eDiary each evening during the pretreatment, treatment, and RW periods. An evening assessment is considered complete if all questions, excluding the weekly assessments, are answered.

eDiary compliance will be calculated for baseline (pretreatment period), the treatment period (weeks 1-12), RW period (RW weeks 1-4), and for each week. For each time period, eDiary percent compliance will be calculated as  $100 * \frac{\text{number of completed evening assessments}}{\text{expected number of days in the period}}$ . Percent compliance will also be dichotomized as  $\geq 80\%$  and  $< 80\%$  for each period, as well as the number and percentage of patients with  $\geq 4$  /  $< 4$  complete eDiary entries each week. Descriptive statistics (number of patients, mean, SD, median, minimum, and maximum) for eDiary compliance will be presented for the ITT population by treatment; n and percent will be presented for the dichotomous categories.

## 7.9 EFFICACY ANALYSIS

All efficacy analyses will be based on the ITT Population for the Treatment Period and based on the RW Population for the RW Period.

Baseline values for efficacy parameters will be derived from the eDiary daily data collected in the Pretreatment Period, specifically the period of time from 14 days prior to randomization up to the time of randomization.

A patient's daily abdominal score is calculated as the average of the daily abdominal pain, abdominal bloating, and abdominal discomfort assessments. If two or more of these individual daily abdominal symptoms are missing, then the Abdominal Score for that day will be missing.

Baseline values for patient symptom severity parameters (e.g., abdominal score, abdominal discomfort, abdominal bloating, abdominal pain, and constipation severity) will be the average of the non-missing severity scores reported during this period.

An SBM is defined as a BM that occurs in the absence of laxative, enema, or suppository use on either the calendar day of the BM or the calendar day before the BM. CSBM is defined as an SBM associated with a sense of complete evacuation.

The baseline CSBM and SBM weekly rates will be derived based on the number of CSBMs and SBMs a patient had during this period.

Baseline stool consistency and straining will be calculated as the average of the non-missing values from the SBMs reported by the patient during this period. A patient's baseline Stool Consistency and straining cannot be assessed if the patient does not have at least one SBM during the Pretreatment Period. Patients with missing baseline Stool Consistency will be excluded from Stool Consistency analyses that involve change from baseline. Similarly, patients with missing baseline straining will be excluded from straining analyses that involve change from baseline.

For weekly responder parameters based on daily eDiary assessments, a patient with less than 4 complete evening reports during an analysis week will not be considered a responder for that week.

Trial centers will be pooled by geographic region (details provided in Section 9.3). In lieu of trial center, geographic region will be used in analyses adjusting for center-to-center variability.

All hypotheses will be tested at a two-sided 0.05 significance level (Section 6.6). All confidence intervals will be 2-sided 95% confidence intervals, unless stated otherwise.

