7. During the time when the Rome III criteria for IBS were met, the patient had hard or lumpy stools (Bristol Stool Form Scale [BSFS] scores of 1 or 2) with at least 25% of BMs and had loose (mushy) or watery stools (BSFS scores of 6 or 7) with less than 25% of BMs in the absence of antidiarrheal or laxative use.
8. Patient reports <3 BMs (with each BM occurring in the absence of any laxative, suppository, or enema use during the preceding 24 hours) per week for at least 12 weeks, before the Screening Visit or before starting chronic treatment with linaclotide (Linzess®), lubiprostone (Amitiza®), polyethylene glycol 3350 (MiraLAX®), plecanatide (Trulance™), or any laxative.
9. Patient has an average score for abdominal pain at its worst of  $\geq 3.0$ , as reported in the eDiary using an 11-point numerical rating scale (NRS) during the 14 days before the Randomization Visit and including the data entry into the eDiary made in clinic at the Randomization Visit prior to randomization.
10. Patient reports  $\leq 6$  complete spontaneous BMs (CSBMs) and  $\leq 10$  spontaneous BMs (SBMs) in the eDiary occurring over the 14 days before the Randomization Visit and including the data entry into the eDiary made in clinic at the Randomization Visit prior to randomization. (Note: A CSBM is an SBM that is associated with a sense of complete evacuation. An SBM is a BM that occurs in the absence of laxative, suppository, or enema use on the calendar day of the BM or the calendar day before the BM as evidenced by the patient-reported laxative use via the eDiary.)
11. Patient is compliant (as defined in the trial procedures section below) with eDiary completion by adequately responding to eDiary questions (ie, completing the daily evening report) on 10 or more of the 14 days before the Randomization Visit.
12. Patient is willing to discontinue any laxatives used before the Pretreatment Visit in favor of the protocol-defined Rescue Medicine (bisacodyl tablets or suppositories).
13. Patient is fluent in English or Spanish.
14. Patient agrees to refrain from making any new, major life-style changes that may affect IBS-C symptoms (eg, starting a new diet or changing his or her exercise pattern) from the time of signature of the ICF to the last trial visit.

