#### **7.9.3.1        *Analyses of Additional Efficacy Endpoints***

All categorical responder parameters (e.g., 6/12 Week CSBM Responder) and SBM within 24 Hours After First Dose, will be analyzed utilizing the same methods defined in Section 7.9.2.1.

All continuous change-from-baseline at each week endpoints and Treatment Satisfaction will be analyzed and summarized using the MMRM approach described in Section 7.9.1.1.

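### SAP 7.9 drops randomized patients with no baseline SBM from the stool-consistency and straining analyses; keeping them needs a missing-baseline rule as well as a weekly-score response

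*SAP*

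**What the plan says.** SAP 7.9 sets the population: "All efficacy analyses will be based on the ITT Population for the Treatment Period". SAP 7.1.3 defines ITT as everyone randomized. Baseline comes from a fixed window, "specifically the period of time from 14 days prior to randomization up to the time of randomization".

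For stool consistency and straining, the baseline is averaged over SBMs only, so it "cannot be assessed if the patient does not have at least one SBM during the Pretreatment Period". Two exclusions follow: "Patients with missing baseline Stool Consistency will be excluded from Stool Consistency analyses that involve change from baseline", and "patients with missing baseline straining will be excluded from straining analyses that involve change from baseline". SAP 5.3.3 places both the BSFS and the 5-point scale under stool consistency, and Protocol 10.4 derives baseline BSFS from SBMs too. I therefore read the rule as covering three endpoints: BSFS, 5-point consistency and straining.

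On the model, SAP 7.9.3.1 says: "All continuous change-from-baseline at each week endpoints and Treatment Satisfaction will be analyzed and summarized using the MMRM approach" of SAP 7.9.1.1. That model has week, treatment, region, week-by-treatment and the baseline value as a covariate. SAP 6.2 keeps the baseline covariate whether the response is a post-baseline score or a change. SAP 6.3 rules out imputation unless it is stated. SAP 7.9.3 classes the three endpoints as additional, outside the formal testing sequence.

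Protocol 6.1, criterion 10, sets a maximum of 10 "spontaneous BMs (SBMs) in the eDiary occurring over the 14 days before the Randomization Visit" and no minimum.

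**The concern.** A patient with no baseline SBM can be randomized, can have SBMs on treatment, and can have up to 12 weekly consistency and straining scores. The plan discards all of them. The analysis is then labelled ITT but describes only randomized patients who had at least one baseline SBM.

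The patients left out are defined by a bowel characteristic that bears on the disease under study, so the result describes a somewhat different population from the one enrolled. Some precision is also lost. Membership of the excluded group is fixed before randomization, so the comparison among those who remain is still a randomized one. Bias is not the issue.

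**Working it through.** **Plan's own figure.** Neither document gives the number or share of patients without a baseline SBM, so there is nothing to reproduce. The stated power concerns the primary and secondary tests and has no bearing here. The only design input used is 600 patients, 300 per group (SAP 4.0).

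**Step 1: how many patients.** Assume baseline SBMs are Poisson with mean m per 14 days. The share with none is exp(−m). Means of 2 to 5 are an assumption. They fit criterion 8 (fewer than 3 laxative-free BMs per week) and the limit of 10 in criterion 10. If keeping a patient adds as much information as any other patient does, the SE falls by 1 − √(1 − share).

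| m | share = exp(−m) | × 600 | 1 − √(1 − share) |
|---|---|---|---|
| 2 | 13.5% | 81 | 7.0% |
| 3 | 5.0% | 30 | 2.5% |
| 4 | 1.8% | 11 | 0.9% |
| 5 | 0.7% | 4 | 0.3% |

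Variation between patients beyond Poisson raises the share at a given mean.

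**Step 2: does the choice of response matter?** Write y for the weekly score and b for baseline. The model y − b = a + βb + τ·treatment is the same as y = a + (β + 1)b + τ·treatment. Only the baseline slope moves, by exactly 1; τ and its SE are identical. This holds only for patients who have b. A patient without b has no change and no covariate value, so either model drops that patient.

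**Step 3: numerical check.** Illustrative data: 600 patients, 12 weeks, some weekly scores missing, true effect 1.2 (arbitrary units), and the MMRM of SAP 7.9.1.1 fitted by maximum likelihood. There is one data set per assumed share, so the last column scatters around the rule in Step 1.

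| Share with no baseline | n used, change or score as response | difference, same for both | SE | score + mean-filled baseline + indicator, n = 600: difference | SE | SE reduction |
|---|---|---|---|---|---|---|
| 2% | 588 | 1.226222 | 0.06268 | 1.236124 | 0.06244 | 0.4% |
| 5% | 570 | 1.231677 | 0.06439 | 1.227369 | 0.06252 | 2.9% |
| 10% | 540 | 1.237211 | 0.06636 | 1.228729 | 0.06267 | 5.6% |
| 20% | 480 | 1.235069 | 0.07015 | 1.215805 | 0.06340 | 9.6% |

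Switching the response alone regains 0 of 60 patients at the 10% share. An ordinary regression with default complete-case handling agrees: 538 of 600 used under both responses, difference 1.253426 under both, and baseline slope −0.531 for change and 0.469 for score.

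**Step 4: dropping the covariate instead.** This keeps everyone but costs precision. At 10%, the difference in the same 540 patients moves from 1.2372 to 1.2558 and the SE rises from 0.06636 to 0.07356 (+10.8%). Even with all 600, the SE is 0.07032, worse than the SAP model on 540.

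**Step 5: what the fill and indicator estimate.** With the indicator in the model, the constant used for the fill does not affect the treatment estimate, because the indicator's coefficient absorbs it. The treatment difference is now pooled over a wider population. At the 10% share it is 1.2287 if the regained patients respond like the others, 1.1744 if their true effect is 0.6, and 1.2831 if it is 1.8. The SAP model gives 1.2372 in all three cases because it never sees them.

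**The case against.** The case for leaving the plan alone has four parts.

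- **Disclosed and inherent.** The endpoint is a change from baseline, which does not exist without a baseline, and SAP 7.9 states the exclusion openly. This stands as a defence of transparency. It does not reconcile the exclusion with the ITT statement in the same section.
- **Low stakes.** The trial's objective is abdominal symptoms. The primary and secondary endpoints use evening abdominal ratings and do not depend on SBMs. In the SBM and CSBM frequency analyses a baseline of zero is a valid rate, so these patients stay in. This stands, and it limits the point to an optional improvement.
- **Uncertain gain.** The share may be below 1%. Treatment weeks without an SBM still yield no consistency or straining score, and patients with no baseline SBM plausibly have more such weeks. The 7% is therefore an upper guide. This stands.
- **Post-randomization dependence.** Whether a regained patient contributes depends on having SBMs on treatment, which treatment may affect. This is true, but it already applies to every patient in these analyses.

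A reader might also infer three stronger things that the documents do not support.

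- The choice of response variable alone causes the exclusion. It does not: the covariate in SAP 7.9.1.1 and 6.2 is missing for the same patients.
- The reported difference would stay the same once they are kept. Equality holds only among patients with a baseline.
- The excluded patients are simply the most constipated. "An SBM is defined as a BM that occurs in the absence of laxative, enema, or suppository use" on that calendar day or the day before, so a patient whose BMs all follow permitted rescue has zero SBMs without having zero BMs. SAP 9.4.2 also treats diary gaps as no BM. The rescue conditions in Protocol 7.7 and the requirement for 10 of 14 evening reports make a severe group plausible, but do not establish it.

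**Conclusion.** The exclusion is real and sits uneasily with the ITT description in the same section. It arises because both the change and the baseline covariate are missing, so a remedy has to deal with both.

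The effect is small: about 4 to 81 of 600 patients, and an SE gain of at most about 0.3% to 7%. Both ranges rest on an assumed Poisson mean of 5 down to 2 SBMs per 14 days. The simulated differences and SEs are illustrations, not forecasts. No bias is shown, and no primary or secondary result is touched. This is a cheap improvement to three additional endpoints; a mean fill with an indicator is one acceptable method among several.

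**What to change.** For the Treatment Period analyses of BSFS, 5-point stool consistency and straining, amend SAP 7.9 and 7.9.3.1 as follows:

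1. Use the weekly score as the MMRM response, with the other terms of SAP 7.9.1.1 unchanged.
2. Where there was no baseline SBM, set the baseline covariate to the overall mean, and add a yes/no fixed effect for no SBM at baseline.
3. Report the LS mean difference and 95% CI. State that it covers all randomized patients with at least one weekly score, and that it may differ from the estimate restricted to patients with a baseline.
4. Keep observed change from baseline as a descriptive table for patients who have one, and report by group how many do not.

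Because SAP 6.3 allows no imputation unless stated, the rule has to be written into the SAP, and before unblinding. Fill and indicator use pre-randomization information only. The cost is wording and minor programming, with no new data. The downside is that LS means appear as scores rather than changes. Patients with no on-treatment SBM still contribute nothing.
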